#### 5.5 Supportive Care:

##### 5.5.1 Prophylactic Anti-Emetic Premedication: 1 hr prior to radiation

Granisetron 2 mg PO  
prochlorperazine 10 mg PO  
promethazine 12.5 mg PO  
or equivalent

##### 5.5.2 Diarrhea

Patients will be instructed to begin taking loperamide after the first poorly formed or loose stool or first episode of 2 or more bowel movements in one day.

Loperamide should be taken in the following manner: 4 mg at the first onset of diarrhea, then, 2 mg after every episode of diarrhea until reaching the daily maximum dose.

Loperamide should not be taken prophylactically.

Patients must notify the research team as to when they initiated loperamide therapy. If diarrhea persists despite loperamide therapy, then the patient should be evaluated for the need for IV fluid & electrolyte replacement.

#### Alternative medications

Somatostatin analog (Octreotide) 100 - 500 mcg SC/IV tid; maximum daily dose = 1500 mcg/day; Alternatively, somatostatin analog may be given at 25-50 mcg/hour as a continuous IV infusion.

Atropine/diphenoxylate which is available as either a 0.025/2.5 tab, or 0.025/2.5 per 5 mL liquid. Patients should take 1-2 tabs PO tid or qid or 5-10 mL PO tid/qid.

Atropine/difenoxin (Motofen) 0.025/1 tab; 2 tabs PO x 1, then 1 tab PO q 2-4 hr (max 8 tabs per day)

Paregoric: (an antidiarrheal opiate): 5 - 10 mL ORALLY 1-4 times daily; maximum 40 mL/day

OTC meds: bismuth subsalicylate 262 mg tabs: 2 tabs PO q 1 hr prn; maximum 4200 mg/24 hr

### 5.5.3 Treatment of Fever & Neutropenia

Subjects developing a fever of 100.5° C or higher will have a CBC with WBC differential obtained along with a history & physical examination to look for signs of infection.

If the ANC is < 500/ $\mu$ L, the patient will be treated with empiric antibiotic therapy as an inpatient & undergo appropriate radiographic & laboratory investigation for sources of infection, & development of a specific treatment plan. Fever & neutropenia occurring during a treatment cycle will require interruption of chemotherapy. The patient may resume chemotherapy at the start of the next scheduled cycle if therapy for infection has been completed & the patient meets other criteria for starting a new cycle

If the ANC is between 500-1000/ $\mu$ L, antibiotic therapy will be instituted if there is clinical suspicion of an infection. Daily CBCs with differentials will be obtained if the patient remains febrile.

If the ANC is > 1000/ $\mu$ L, & there is no clinical evidence of an infection, then therapy may resume.

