## **Section 3.0 Eligibility Criteria**

### **3.1 Inclusion Criteria:**

Patients must meet all the following criteria

- 3.1.1 Male or female patients  $\geq$  19 years of age
- 3.1.2 A life expectancy of at least 12 weeks with a Karnofsky performance status  $\geq$  60% (Appendix V)
- 3.1.3 Histologically or cytologically documented HCC
- 3.1.4 The target lesion can be accurately measured in at least one dimension according to RECIST and must have a maximum tumor diameter of  $\leq$  8 cm

- 3.1.5 Previous systemic chemotherapy or non-radiation local therapy (such as surgery, hepatic arterial therapy, chemoembolization, radiofrequency ablation, percutaneous ethanol injection or cryoablation) is allowed. Local therapy must be completed at least 6 weeks prior to the baseline scan.
- 3.1.6 Cirrhotic status of Child-Pugh class A and B (Appendix I)
- 3.1.7 Platelet count  $\geq 60 \times 10^9/L$ , Hemoglobin  $\geq 8.5$  g/dL, WBC  $\geq 2000/\mu L$
- 3.1.8 International normalized ratio (INR) must be  $\leq 2.3$ . Patients who are being therapeutically anticoagulated with an agent such as Coumadin or heparin will be allowed to participate provided that no prior evidence of underlying abnormality in these parameters (PT, PTT, INR) exists.
- 3.1.9 Must be aware of the neoplastic nature of his/her disease and willingly provide written, informed consent after being informed of the procedure to be followed, the experimental nature of the therapy, alternatives, potential benefits, side-effects, risks and discomforts.

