#### 5.5 Dose Modifications:

Radiation therapy will be held if the AGC is  $< 500/\mu\text{L}$  and/or the platelets are  $< 50,000/\mu\text{L}$ . Upon recovery of the AGC to  $\geq 500/\mu\text{L}$  and platelets to  $> 50,000/\mu\text{L}$ , radiation therapy will resume at the full planned daily dose.

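### Section 5.5.3 prints the fever trigger as 100.5° C and ties its interrupt-and-resume rule to chemotherapy cycles, in a trial that gives only five SRT fractions

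*Combined protocol and SAP*

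**What the plan says.** Section 5.5.3 (Treatment of Fever & Neutropenia) opens with the trigger: "Subjects developing a fever of 100.5° C or higher will have a CBC with WBC differential obtained". It then branches on the neutrophil count.

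- **ANC below 500/µL:** inpatient empiric antibiotics, a search for the source of infection, and a specific treatment plan. Then: "Fever & neutropenia occurring during a treatment cycle will require interruption of chemotherapy". Restarting is covered by "The patient may resume chemotherapy at the start of the next scheduled cycle if therapy for infection has been completed", with the further condition that the criteria for a new cycle are met.
- **ANC 500-1000/µL:** antibiotics on clinical suspicion and daily counts while febrile. No rule for restarting treatment is given.
- **ANC above 1000/µL:** if "there is no clinical evidence of an infection, then therapy may resume". The therapy is not named.

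The rule that names radiation is in Dose Modifications: "Radiation therapy will be held if the AGC is" below 500/µL and/or platelets are below 50,000/µL. Once AGC is at least 500/µL and platelets exceed 50,000/µL, "radiation therapy will resume at the full planned daily dose". Fever and infection are not mentioned there.

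Section 8.0 states that the study uses no drugs, and Section 10.1 describes every dose level as five fractions. Dose Modifications is numbered 5.5, and so is the next heading, "5.5 Supportive Care", which contains 5.5.3.

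**The concern.** Two operative parts of a safety rule do not fit this trial. The trigger carries a unit that makes it unreachable if taken literally. The instructions on stopping and restarting refer to chemotherapy and cycles, neither of which the protocol provides.

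The practical question is whether a patient recovering from febrile neutropenia, but still under treatment for infection, should receive the next fraction of 8 to 14 Gy. The protocol gives no single answer. The sentence that would say to wait concerns a different treatment, and the sentence that does concern SRT makes restarting the default once counts recover.

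The trigger also matters for how a count is obtained. As the tables were read, Appendix II schedules no CBC at the start or end of SRT, and Section 7.1 lists it at baseline, after SRT and at follow-up. The fever-triggered CBC is then the main written route to an ANC between fractions, and the Dose Modifications hold can act only once a count exists.

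**Working it through.** No sample size, error rate or escalation probability enters here. The check is a unit conversion, a side-by-side reading, and a count of days for the remedy.

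**1. The trigger.** Input: 100.5, printed with unit C (Section 5.5.3).

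- Read as Celsius: 100.5 × 9/5 + 32 = 180.9 + 32 = 212.9° F, which no patient can reach.
- Read as Fahrenheit: (100.5 − 32) × 5/9 = 68.5 × 5/9 = 38.06° C, a plausible fever threshold.

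**2. The treatment being interrupted.** Sections 8.0 and 10.1 together leave SRT as the only protocol treatment. There is no cycle and no set of criteria for starting one, so the ANC < 500 restart condition has nothing to act on.

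**3. What each rule says about restarting SRT.** Take a patient who had fever with ANC below 500/µL, whose platelets are now above 50,000/µL, and who is still on antibiotics. AGC and ANC are treated as the same quantity; the available text spells out neither.

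| Rule | Count now 600/µL | Count now above 1000/µL, no clinical signs of infection |
|---|---|---|
| Dose Modifications | SRT resumes at full dose | SRT resumes at full dose |
| Last line of 5.5.3, if it means SRT | Not yet | May resume |
| Chemotherapy sentences of 5.5.3 | Would wait, but do not name SRT | Would wait, but do not name SRT |

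In the first column, two rules that may both govern SRT give different answers (AGC ≥ 500 against ANC > 1000). In the second, both permit SRT during infection treatment, and only the misdirected sentences would delay it.

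**4. Effect of redirecting the condition to SRT.** The length of an antibiotic course is not in the documents, so 7, 10 and 14 days are assumed, with the hold lasting as long as the course. Five treatment days are added and compared with the two-week (14-day) delivery period in the Abstract and Section 5.2.2:

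- 7 + 5 = 12 days: can fit.
- 10 + 5 = 15 days: exceeds 14.
- 14 + 5 = 19 days: exceeds 14.

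DLT item (e) in Section 10.1 counts an interruption of at least 14 calendar days. Holds of 7 and 10 days stay below it; a 14-day hold reaches it.

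**The case against.** The strongest reply is that the protocol already protects the patient. No clinician would wait for 100.5° C, so the unit corrects itself in use, and the text was machine-read, so a misread F cannot be fully excluded. Dose Modifications stops SRT in any patient with AGC below 500/µL. The usable part of 5.5.3 requires admission, investigation and an individual treatment plan. Since SRT is the only protocol treatment, *therapy* in the last line most naturally means SRT, so an infection condition for febrile patients already exists. Section 5.6 lists investigator judgment as a ground for ending treatment. Section 9.3 adds stopping for unacceptable toxicity, weekly review during SRT, and real-time faxing of outside laboratory results.

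Most of this stands, and it keeps the point small. It does not remove it. The last line asks for no clinical evidence of infection, which is not the same as finished infection treatment, and its threshold differs from the one in Dose Modifications. None of the general safeguards says that infection treatment must end before the next fraction.

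A second objection is that requiring finished infection treatment is a clinical rule for SRT, not a pure word swap. That is fair, and its effect on treatment time has to be counted as a cost.

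**Conclusion.** Section 5.5.3 is wrong as written in two operative places: the unit of the trigger, and the treatment to which the interrupt-and-resume rule applies. The severity is minor. What remains unprotected is narrow: restarting SRT on recovered counts while an infection is still being treated, with an unresolved choice between 500 and 1000/µL for febrile patients. No DLT definition, sample size or operating characteristic changes. The frequency of febrile neutropenia during five fractions is not in the documents, so the number of patients affected cannot be estimated. The unit point assumes that the source PDF prints C.

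Three stronger readings are not supported:

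- A reader might infer that a febrile patient with ANC below 500/µL could go on receiving SRT. Dose Modifications holds it once the count is known.
- A reader might infer that infection from the marker implant makes this scenario likely. Section 5.4.1 lists infection as a risk, but nothing links it to neutropenia. Section 5.1 provides prophylactic antibiotics, and Appendix II schedules examinations and counts after the implant and at planning.
- A reader might infer from the lack of an ANC minimum in Section 3.1.7 that patients commonly enter below 1000/µL. The criterion makes that possible; no frequency is given, and it has no bearing on which treatment 5.5.3 names.

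**What to change.** Amend Section 5.5.3 only:

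- Set the trigger at 100.5° F (38.1° C).
- Replace the two chemotherapy sentences with wording such as: *If fever and neutropenia occur during SRT, SRT is interrupted; the remaining fractions may be given once infection treatment is finished and the counts meet the criteria under Dose Modifications.* Cite that section by its heading, because the number 5.5 is used twice.
- Write *SRT* for *therapy* in the last line, and have the investigators state whether ANC above 1000/µL or AGC of at least 500/µL governs febrile patients. That also settles when patients in the 500-1000/µL branch may restart.

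This adds no patients, visits or tests. The cost is a longer hold in a few febrile neutropenic patients. On the assumed courses, 10 or 14 days would push delivery past two weeks, so the investigators should accept that knowingly. A 14-day hold would count as a DLT only if the event is at least possibly related to SRT and falls within 30 days of starting treatment. DLT item (e) itself needs no change.

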#### 5.5.4 Blood Products

Blood product support will utilize packed red blood cells or platelets if clinically indicated

#### 5.5.5 Nutritional Supplementation

Patients will be encouraged to drink specialized cancer supplement between meals.

### 5.6 Criteria for removal of patients from study

#### 5.6.1 Disease progression

#### 5.6.2 Study closure

#### 5.6.3 Any dose limiting toxicity (defined at section 10.1)

#### 5.6.4 Patient decision to withdraw from the study, or

In the judgment of the investigator, further treatment would not be in the best interest of the patient.

## Section 6.0 Measurement of Effect

### 6.1 Toxicity criteria

The NCI Common Toxicity Criteria Adverse Events version 3 will be used to grade toxicity; it is available at the following internet site:

<http://ctep.cancer.gov/forms/CTCAEv3.pdf>.

### 6.2 Clinical Benefit Response

Clinical benefit response is a measure of clinical improvement based on analgesic consumption, pain intensity, performance status and weight change.

A patient is considered a clinical benefit responder if either:

6.2.1 The patient shows a  $\geq 50\%$  reduction in pain intensity or analgesic consumption (Appendix IV: Pain assessment)

OR

6.2.2 Improvement in performance status (Appendix V) of  $\geq 20$  points for a period of at least four consecutive weeks, without showing any sustained worsening in any of the other parameters (sustained worsening was defined as four consecutive weeks with either any increase in pain intensity or analgesic consumption or a  $\geq 20$  point decline in performance status)

OR

6.2.3 The patient is stable on all of the aforementioned parameters, and shows a marked, sustained weight gain ( $\geq 7\%$  increase maintained for  $\geq 4$  weeks) not due to fluid accumulation

## 6.3 Tumor Response

6.3.1 Measurable Disease Response: CTEP's RECIST guidelines will be followed. A quick reference to the RECIST guidelines can be downloaded at the following URL: <http://ctep.info.nih.gov/Policies/WordDocs/RCSTF.PH2TEMPF.doc>. (Appendix III)

Patients enrolled in this study must have a measurable HCC which is defined as lesions that can be accurately measured in at least one dimension: [longest diameter to be recorded] on the CT scan or MRI scan.

The same method of assessment & the same technique should be used to characterize each identified & reported lesion at baseline & during follow-up.

Parameters to Measure Response Outcome:	
1	Clinical examination
2	CT scan
3	MRI scan
4	AFP

### 6.3.2 Response criteria

6.3.2.1 Taking into account the measurement of the longest diameter only for those lesions with size response, response criteria are defined as:

Complete Response (CR): the disappearance of a lesion.

Near Complete Response (NCR): at least an 80% decrease in the longest diameter of a lesion, taking as reference the longest diameter recorded since the treatment started.

Partial Response (PR): at least a 30% decrease in the longest diameter of a lesion, taking as reference the longest diameter recorded since the treatment started.

Progressive Disease (PD): at least a 25% increase in the longest diameter of a lesion, taking as reference the longest diameter recorded since the treatment started.

Stable Disease (SD): neither sufficient shrinkage to qualify for partial response nor sufficient increase to qualify for progressive disease, taking as reference the longest diameter since the treatment started.

6.3.2.2 The criteria used to determine the objective tumor response for those lesions without size response:

Complete Response (CR): the normalization of AFP level.

Partial Response (PR): at least a 25% decrease in the AFP level.

Progressive Disease (PD): the maintenance of AFP level above the normal limits

In some circumstances, it may be difficult to distinguish residual disease from the radiation induced necrotic tissue. When the evaluation of complete response depends on the normalization of AFP level, it is recommended that the residual lesion be investigated (fine-needle aspiration/biopsy) before confirming the complete response status.)

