### Methods of Measurement –

- CT and MRI are the best currently available and reproducible methods to measure target lesions selected for response assessment. Conventional CT and MRI should be performed with cuts of 10 mm or less in slice thickness contiguously. Spiral CT should be performed using a 5 mm contiguous reconstruction algorithm. This applies to tumors of the chest, abdomen and pelvis. Head and neck tumors and those of extremities usually require specific protocols.
- Lesions on chest X-ray are acceptable as measurable lesions when they are clearly defined and surrounded by aerated lung. However, CT is preferable.
- When the primary endpoint of the study is objective response evaluation, ultrasound (US) should not be used to measure tumor lesions. It is, however, a possible alternative to clinical measurements of superficial palpable lymph nodes, subcutaneous lesions and thyroid nodules. US might also be useful to confirm the complete disappearance of superficial lesions usually assessed by clinical examination.
- The utilization of endoscopy and laparoscopy for objective tumor evaluation has not yet been fully and widely validated. Their uses in this specific context require sophisticated equipment and a high level of expertise that may only be available in some centers. Therefore, the utilization of such techniques for objective tumor response should be restricted to validation purposes in specialized centers. However, such techniques can be useful in confirming complete pathological response when biopsies are obtained.
- Tumor markers alone cannot be used to assess response. If markers are initially above the upper normal limit, they must normalize for a patient to be considered in complete clinical response when all lesions have disappeared.
- Cytology and histology can be used to differentiate between PR and CR in rare cases (e.g., after treatment to differentiate between residual benign lesions and residual malignant lesions in tumor types such as germ cell tumors).

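### Section 6.3.2 conflicts with the RECIST rules that 6.3.1 adopts, gives one AFP result two opposite classes, and the CT size-change objective has no CT scheduled after SRT

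*Combined protocol and SAP*

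**What the plan says.** **Standard adopted.** Section 6.3.1 states that "CTEP's RECIST guidelines will be followed" and refers to Appendix III. It accepts CT or MRI for measurement and adds: "The same method of assessment & the same technique should be used to characterize each identified & reported lesion at baseline & during follow-up".

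**Size criteria (6.3.2.1).** These are worded for a single lesion. Progression is "at least a 25% increase in the longest diameter of a lesion, taking as reference the longest diameter recorded since the treatment started". New lesions are not mentioned. There is an extra class, "Near Complete Response (NCR): at least an 80% decrease in the longest diameter of a lesion", which Appendix III does not have.

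**AFP criteria (6.3.2.2).** For lesions without size response, AFP sets the class. Normalization is complete response. The other two classes are "Partial Response (PR): at least a 25% decrease in the AFP level" and "Progressive Disease (PD): the maintenance of AFP level above the normal limits". A needle aspirate or biopsy is recommended before a complete response that depends on AFP is confirmed.

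**Appendix III.** It says "Tumor markers alone cannot be used to assess response", and it classes a marker that stays above normal as incomplete response/stable disease. Partial response is a fall of at least 30% in the summed longest diameters from baseline. Progression is a rise of at least 20% over the smallest sum, or a new lesion.

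**Objectives, schedule and analysis.** Objective 1.2.2.1 is percentage size change on CT, 1.2.2.2 is intensity change on MRI, and 1.2.2.3 is change in AFP. Section 7.1 and Appendix II each give an imaging schedule. Section 10.4 plans radiological complete and partial response rates at the MTD with 90% exact intervals.

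**The concern.** The protocol holds two sets of response rules and does not rank them. Two assessors who each follow the text can put the same patient in different classes, and under 6.3.2.2 a single assessor can put one AFP result in two opposite classes. One listed secondary objective has no scheduled follow-up measurement.

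Response data are a stated purpose of the 10-patient expansion (10.1, 10.2), so the class definitions matter for what the trial can report. Disease progression is also a ground for removal from study (5.6.1), and the protocol gives more than one definition of it.

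**Working it through.** The plan states no figure on this point, so there is none to reproduce. The check sets the passages side by side and uses illustrative values. All lesion sizes and AFP values below are assumptions.

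**1. AFP (6.3.2.2 against Appendix III).** Take AFP from 400 to 200 with a normal limit below 200 and no size response.
- Change: 200/400 − 1 = −50%. This is a fall of at least 25%, so partial response.
- 200 is still above normal, so progressive disease.
- There is no precedence rule and no stable class in 6.3.2.2.
- Under Appendix III the marker alone gives no response, and a marker still above normal is incomplete response/stable disease.

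Routing is also open. Section 6.3.2.1 has its own stable class, so a lesion of unchanged size with a raised, unchanged AFP is stable if scored there and progressive if scored under 6.3.2.2.

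**2. Size progression (6.3.2.1 against Appendix III).** Take one lesion, 50 mm as reference, and one later scan at 61 mm.
- Change: 61/50 − 1 = +22%.
- Appendix III threshold: 1.20 × 50 = 60.0 mm, so progressive.
- Section 6.3.2.1 threshold: 1.25 × 50 = 62.5 mm, so stable.
- From 50 mm, the disputed band runs from 60.0 mm to just under 62.5 mm.

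This holds if non-shrinking lesions are scored under 6.3.2.1. If they are routed to 6.3.2.2, AFP decides instead, which is a different departure from Appendix III.

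The reference matters separately. Take a lesion recorded at 60 mm at its longest and later at 40 mm. This needs at least two scans after SRT, which only 7.1 provides.
- Appendix III: progressive from 1.20 × 40 = 48 mm.
- Section 6.3.2.1, reference read as a maximum over time: 1.25 × 60 = 75 mm.
- Section 6.3.2.1, reference read as the smallest value: 1.25 × 40 = 50 mm.

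For partial response in a single lesion, the two texts differ if the 6.3.2.1 reference is a maximum over time or if it excludes the pre-treatment scan. Otherwise they agree.

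**3. Several lesions.** The abstract requires at least one tumor within the size limit, and 5.2.3 refers to a cumulative GTV, so a patient may have more than one lesion. Take two measurable lesions, 50 to 34 mm and 40 to 40 mm.
- By lesion: 34/50 − 1 = −32% (partial response) and 0% (stable, if scored under 6.3.2.1).
- By patient under Appendix III: (34 + 40)/(50 + 40) = 74/90 = 0.822, a fall of 17.8%, so stable.
- Section 6.3.2 gives no rule for combining the two lesion results.

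**4. Scans against objectives.**

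| | Section 7.1 | Appendix II |
|---|---|---|
| CT | baseline, simulation | screening, marker implant, SRT planning |
| CT after SRT | none | none |
| MRI after SRT | post-SRT, 1 month, 3 months | 3 months only |

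Objective 1.2.2.1 therefore has no scheduled follow-up CT. Pairing a baseline CT with a follow-up MRI would break the same-method rule in 6.3.1. With a single MRI after SRT, the repeat assessment at least 4 weeks later that Appendix III asks for cannot be made.

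**The case against.** **Deliberate adaptation.** Section 6.3.2 may be a study-specific, lesion-level scheme for a local treatment; its remark on radiation necrosis points that way. This is plausible, but no text says that it overrides RECIST, and it would not cure the AFP overlap.

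**Little reaches the planned analysis.** This stands. Section 10.4 is limited to radiological responses, so a reader who inferred that AFP-only responses inflate that rate would go beyond the text. The progression band does not enter it either. The outputs listed under 1.2.2 are percentage changes, and near complete response already satisfies the 30% rule for partial response.

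**Unit of analysis.** One might infer that lesions would be counted as independent units in the exact binomial interval. The documents do not support this: 10.1 and 10.2 enrol patients for response data, so the rate is most naturally per patient. Sections 3.1.4 and 5.1 also speak of one target lesion and one tumor. What stands is the missing rule for a patient with several lesions.

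**Biopsy safeguard.** It exists, but it is a recommendation and covers only AFP-based complete response.

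**MRI can measure size.** Correct under 6.3.1, so size response is assessable. Only the CT-specific objective lacks data.

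**Removal from study.** Under Appendix II the only MRI after SRT is at 3 months, the last visit named in 5.3, so the effect through 5.6.1 may be small. The passages still conflict.

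**Conclusion.** The concern holds as a set of wording and schedule defects in a secondary, descriptive endpoint. Two parts are firm on the plain text: the AFP classes overlap and contradict Appendix III, and no CT after SRT is scheduled for objective 1.2.2.1. The progression threshold, its reference and the new-lesion rule also differ from Appendix III, although the 50 to 61 mm example depends on non-shrinking lesions being scored by size. The multi-lesion gap is real but limited to patients with several lesions.

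How many patients would change class cannot be derived from the documents. Dose escalation rests on dose-limiting toxicity and is unaffected. The difference between the 90% interval in 10.4 and the 95% in Appendix III might be read as a further conflict, but 10.4 specifies the interval for this trial, so it is not part of this point. The defects should be corrected; they do not threaten the primary safety objective.

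**What to change.** - Remove 6.3.2.2 as a route to objective response and report AFP change only under 1.2.2.3. Align the abstract and the 6.3.1 parameter list, which name AFP as a response measure.
- State that, for response reporting, the Appendix III definitions replace those in 6.3.2.1: partial response against baseline, and progression by its threshold, smallest-sum reference and new-lesion rule. Count near complete response within partial response.
- State in 10.4 that the rate is imaging-based with one result per patient. Summed diameters make this a whole-patient measure, in which unirradiated and new lesions count. If treated-lesion response is intended, label it so and report RECIST patient response alongside.
- Restate 1.2.2.1 as size change on MRI, using baseline and follow-up MRI. MRI is already needed for 1.2.2.2, and this adds no procedure for research, in keeping with 5.3.
- Reconcile the MRI rows of 7.1 and Appendix II. Report responses without a repeat scan as unconfirmed, as Appendix III provides.
- Reconcile the progression passages that bear on removal from study (5.6.1). No clinical rule is proposed here.

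The cost is a wording amendment using rules and scans already in the protocol. The reported response rate may be lower, and if treated-lesion response is kept, two summaries are needed.
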